## **6.3 Safety Evaluations**

Participants will be fasting for a minimum of 10 hours prior to the study visit. This may cause hunger pangs, upset stomach, headache, or light-headedness. If the participant shows any signs of clinical instability or definitively decides to discontinue participation, the study visit will be ended.

The patient will be notified of any clinically relevant abnormal test result(s) performed. It will be recommended that results, especially abnormal results, be discussed by the guardian with the participant’s primary care physician.

## 7 STATISTICAL CONSIDERATIONS

### 7.1 Primary Endpoint

We will determine the completeness of CGM data capture and adequacy of nutrition logs for evaluation of at-home glucose challenge.

### 7.2 Secondary Endpoints

Secondary endpoints include test performance characteristics of at-home CGM-measured glucose challenge as compared with gold-standard laboratory-based 2-hour OGTT; acceptability of use of CGM for at-home dysglycemia evaluation as an alternative to 2-hour lab-based OGTT.

### 7.3 Control of Bias and Confounding

Potentially eligible subjects will be stratified by sex and age (8-14, 15-18), and an equal number of participants will be contacted per group until recruitment goals are reached or all potentially eligible subjects in a category are enrolled or decline to participate.

Multivariable models will adjust for covariates including age, sex, race, ethnicity, and anthropometrics (e.g. BMI-Z).

### 7.4 Statistical Methods

#### 7.4.1 Analysis of Primary and Secondary Outcomes of Interest

Primary objective: Determine the feasibility of at-home, CGM-based glycemia evaluation as measured by adequacy of CGM data capture and nutrition logging quality and completion on days of at-home glucose and mixed-meal challenge.

*H1a: Complete CGM data will be available for  $\geq 80\%$  of requested days worn:* The number of days with adequate CGM data will be divided by 9, omitting the first 24 hours due to possible inconsistent measurements after initial placement. Feasibility will be defined as  $\geq 80\%$  (7.2) of days with data.

*H1b: Documentation of glucose and mixed-meal challenge will be complete and adequate for analysis for  $\geq 80\%$  of participants:* The number of participants who document the date and time of glucose and mixed-meal ingestion (including mixed-meal content) will be determined and divided by the total number of participants. Feasibility will be defined as  $\geq 80\%$  of participants documenting date and time of either the glucose challenge, mixed-meal challenge, or both.

Secondary objective: Determine the test performance characteristics of at-home, CGM-measured glucose challenge with laboratory-based 2-hour OGTT.

*H2: CGM-measured glucose 2 hours and 5 minutes after standardized glucose ingestion will have adequate discrimination of normal ( $<140$  mg/dL) versus dysglycemic ( $\geq 140$  mg/dL) 2-hour OGTT glucose, as assessed by area under the receiver operating characteristic curve  $\geq 0.7$ :* Using participant logs via text message survey or paper-based logs, date and time of home glucose challenge will be determined and labeled in CGM data. A time point 2 hours and 5

---

minutes later (accounting for lag due to interstitial measurement)(Wadwa, Laffel et al. 2018) (CGM-2h) will serve as the comparison to the 2-hour glucose during OGTT obtained at the study visit (OGTT-2h). Sensitivity, specificity, and positive and negative predictive values of CGM-2h to predict OGTT-2h $\geq$ 140 mg/dL will be assessed for various thresholds of CGM-2h. Area under the receiver operating characteristic curve (AUC) will be determined. An AUC threshold of  $\geq$ 0.7 will be used to define adequate discrimination. The same analysis will be repeated for the comparison of baseline CGM glucose (at time of glucose ingestion) to fasting glucose on OGTT, using a fasting glucose threshold of  $\geq$ 100 mg/dL to define dysglycemia. Finally, correlation analyses (Spearman or Pearson depending on distribution) will be performed to further explore the relationship between CGM indices obtained during at-home glucose challenge (e.g., baseline, peak, mean glucose) and both laboratory-measured HbA1c and plasma glucose during OGTT. Correlations will be examined across subgroups such as lower versus higher ActiGraph-measured physical activity level and self-reported carbohydrate intake on the day prior to at-home glucose challenge, age, pubertal stage, and body mass index.

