Key criteria for Inclusion and Exclusion:	
 
1. Any gender, age 8-18 years
 
2. Tanner 2 or higher pubertal development
 
3. Overweight or obese (BMI <math>\geq 85^{\text{th}}</math> percentile for age/sex, or <math>\geq 25 \text{ kg/m}^2</math> for participants <math>\geq 18</math> years)
 
4. A) No previously documented abnormal HbA1c or glucose but at higher risk for T2D based on race/ethnicity (Black, Hispanic, Asian, Native American, Pacific Islander), diagnosis with dyslipidemia, hypertension, polycystic ovary syndrome, presence of acanthosis nigricans, or first degree relative with T2D (n = 15); or B) previously documented (within 6 months) HbA1c 5.7-7.0%, fasting glucose <math>\geq 100 \text{ mg/dL}</math>, or 2-hour plasma glucose on OGTT of <math>\geq 140 \text{ mg/dL}</math> (n = 25)
 
5. Consent (adult subjects), parental/guardian permission (if applicable), assent (if applicable)
 
6. Willingness to wear ActiGraph watch and CGM continuously for 10 day study duration
 

	Exclusion Criteria
	
 
1. Current or recent (within 1 month) use of diabetes-related medication
 
2. Current use of hydroxyurea (due to interference with CGM)
 
3. Known type 1, cystic fibrosis-related, or medication-induced diabetes
 
4. Potential subject unable to speak or read in English
 
5. Severe cognitive impairment
 
6. Current or previous pregnancy
 

Number Of Subjects	40 total, all at Children's Hospital of Pittsburgh
Study Duration	Each participant will attend 1 in-person study visits that will last 2.5-3 hours, followed by 10 days of continuous CGM wear at home. The entire study is expected to last approximately 1 year, from July 1, 2022 – June 30, 2023.

---

---

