**Study Phases**

**Screening and recruitment:** Potential subjects will be identified via review of Endocrinology clinic schedules weekly and by using the Research Interest Form distributed by Adolescent medicine. After potential subjects are identified, they will be contacted along with their parents/guardians (as applicable), to screen for eligibility. Subjects will be consented and will be scheduled for a morning study visit at the Pediatric Clinical and Translational Research Center (PCTRC). They will be instructed to complete an overnight 10 hour fast at home prior to the study visit.

**Study Visit 1:** Participants will undergo physical examination by a pediatric endocrinologist, anthropometrics, vital signs measurement, questionnaires (medical, family, social history), and 2-hour oral glucose tolerance test (OGTT). Dexcom G6 Pro (blinded, no data visible to participant) CGM will be placed on the participant's abdomen by trained study staff. Participants (or their parent) will be registered for text message-based surveys and will be instructed on nutrition, activity, and sleep logging to be completed during the 10-day CGM wear period. Participants will be provided with a wrist-worn actigraphy device (ActiGraph GT9X Link) to wear continuously during the 10-day period for collection.

**10-day Observation Period:** Participants will be instructed to participate in their typical daily routines, with the exception of two at-home challenges: 1) glucose, and 2) mixed-meal. The ***at-home glucose challenge*** will serve as the primary comparison to the laboratory-measured OGTT. For this challenge, participants will be asked to drink the same glucose solution (Trutol) consumed as part of the OGTT at PCTRC and provided with the appropriate weight-based amount. They will be instructed to choose a day between days 3 and 9 of the study period during which they will be able to fast for at least 10 hours, drink the glucose beverage over the course of 5 minutes, and then be inactive for 2 hours. They will log the date and time of glucose ingestion. For the ***at-home mixed-meal challenge***, participants will be asked to choose a day between study days 3 and 9, separate from the glucose challenge day, during which they will be able to fast for at least 10 hours, eat a snack or meal with at least 50 grams of carbohydrate as well as fat and protein content, and then be inactive for 2 hours. All participants and families will be instructed on

---

---

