**Statistical And Analytic Plan**

Demographic and clinical characteristics will be described using summary statistics, including means, standard deviations, medians, and ranges for continuous variables, and frequencies for categorical variables. Analyses will be conducted using Stata 17 (StataCorp, College Station, TX). Raw actigraphy data will be processed using GGIR, a package in R: A language and environment for statistical computing (R Corp Team, Vienna, Austria). The significance level for two-sided hypothesis testing will be set at 0.05.

To assess completeness of CGM data, the number of days with adequate CGM data will be divided by 9, omitting the first 24 hours due to possible inconsistent measurements after initial placement. Feasibility will be defined as  $\geq 80\%$  (7.2) of days with data. To assess completeness of glucose and mixed-meal challenge documentation, the number of participants who document the date and time of glucose and mixed-meal ingestion (including mixed-meal content) will be determined and divided by the total number of participants (40). Feasibility will be defined as  $\geq 80\%$  of participants documenting date and time of either the glucose challenge, mixed-meal challenge, or both. To evaluate test performance characteristics, sensitivity, specificity, and positive and negative predictive values of glucose on CGM 2 hours after at-home glucose beverage ingestion (CGM-2h) to predict OGTT-2h $\geq 140$  mg/dL will be assessed for various thresholds of CGM-2h. Area under the receiver operating characteristic curve (AUC) will be determined. An AUC threshold of  $\geq 0.7$  will be used to define adequate discrimination. Acceptability will be rated on a Likert scale (1: completely unacceptable, 2: mostly unacceptable, 3: neutral, 4: mostly acceptable, 5: completely acceptable). Acceptability will be defined as a mean score for all participants of  $\geq 3$ . Interview transcripts will be reviewed by study staff trained in qualitative analysis. Content analysis will be used to identify themes and sub-themes.

---

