#### 4.1.2 Study Visit

After study procedures are reviewed and questions answered, written informed consent and assent (participants<18) will be obtained if not already obtained electronically via REDCap. Participants will arrive after overnight fast (minimum 10 hours) and will undergo physical examination by a pediatric endocrinologist as well as anthropometrics, vital sign measurement, questionnaires (medical, family, social history), and 2-hour OGTT performed according to American Diabetes Association criteria.(American Diabetes Association Professional Practice, American Diabetes Association Professional Practice et al. 2022) After baseline (time 0) venous blood sample, participants will ingest glucose solution (1.75 g/kg body weight, max 75g) within 5 minutes or less. Additional venous blood samples will be obtained at timed intervals after ingestion to determine plasma glucose, insulin, and c-peptide

(30, 60, 90, 120 min) . HbA1c will also be measured (one venous blood sample). During OGTT, Dexcom G6 Pro (blinded, no data visible to participant) CGM will be placed on the participant's abdomen by study staff trained in CGM placement. Participants will be assigned a unique study ID for use with Dexcom and survey collection. Participants (or their parent if the participant does not have a phone with text messaging capability) will also be registered for text message-based surveys via Mosio, a text messaging platform for clinical research, and will be instructed on nutrition, activity, and sleep logging to be completed during the 10-day CGM wear period. Paper logbooks will be provided for use in case of technical difficulties with texts. Participants will be provided with a wrist-worn actigraphy device (ActiGraph GT9X Link) to wear continuously during the 10-day period for collection of objectively measured activity and sleep data to define periods of eating, overnight fasting, and exercise.

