### **4.2 Study Duration, Enrollment and Number of Sites**

#### **4.2.1 Duration of Subject Study Participation**

The study visit is expected to take approximately 2.5-3 hours. CGM will be worn for 10 days, beginning the day of the study visit. The phone interview is expected to take approximately 30 minutes. The phone call will take place no more than 4 weeks after the study visit.

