### **5.2 Study Visit**

- Vital signs (heart rate, blood pressure): 5 minutes
- Urine pregnancy test (all females): 3 minutes

- Height, weight, waist and hip circumference: 5 minutes
- Focused physical exam, including pubertal status: 5 minutes
- Fasting 2-hour oral glucose tolerance test: 120 minutes
  - Medical, surgical, family, social history: 10 minutes (during OGTT)
  - Provide ActiGraph device, instruct on use: 5 minutes (during OGTT)
  - Place CGM on abdomen, instruct on use: 5 minutes (during OGTT)
  - Review instructions for glucose and mixed meal challenge, including food label interpretation for carbohydrate content: 10 minutes (during OGTT)
  - Enroll in text messaging platform, instruct about survey completion: 5 minutes (during OGTT)
  - Provide addressed, pre-paid shipping envelope to return CGM, ActiGraph

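### H1a divides adequate CGM days by 9, but the scheduled wear leaves only about 8.0–8.2 elapsed days after the first 24 hours, so on that reading the 80% bar is really 88–90%

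*Combined protocol and SAP*

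**What the plan says.** Section 7.4.1 introduces H1a with the words "Complete CGM data will be available for" at least 80% of the requested days. The operative rule follows: "The number of days with adequate CGM data will be divided by 9, omitting the first 24 hours", because early readings may be inconsistent. The bar is 80%, given in brackets as 7.2. The synopsis (Statistical And Analytic Plan) repeats it: "the number of days with adequate CGM data will be divided by 9". Section 6.2 gives the 80% without the divisor.

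The length of wear is described in two ways.

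- **As ten days.** Section 4.2.1: "CGM will be worn for 10 days, beginning the day of the study visit". Synopsis, Study Duration: "followed by 10 days of continuous CGM wear at home".
- **By its start and end.** Participants are "scheduled for a morning study visit" (synopsis, Study Phases). Section 4.1.2 says "During OGTT, Dexcom G6 Pro (blinded, no data visible to participant) CGM will be placed on" the abdomen, and section 5.2 agrees: "Place CGM on abdomen, instruct on use: 5 minutes (during OGTT"). Table 1 numbers the visit as Day 1, and the heading of section 5.3 runs the observation period over Days 1 to 10. Section 5.3.4 has the sensor taken off at midday on the tenth day.

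The documents do not define an adequate day. They do not say whether a day is a calendar day or a 24-hour period, or how a partly covered day counts.

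**The concern.** The rule removes 24 hours, not Day 1. Nine full days remain after that cut only if the sensor is worn for 240 hours, and the stated start and end do not give 240 hours. The divisor then exceeds what a fully adherent participant can supply, and the percentage cannot reach 100.

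H1a is one of the two primary feasibility criteria. On this reading the bar is stricter than the 80% written in sections 7.4.1 and 6.2, so the approach could be reported as not feasible although more than 80% of the obtainable data were captured. How flawless wear scores would also depend on a counting rule that the plan leaves open.

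**Working it through.** **Plan's own figure.** 0.80 × 9 = 7.2. It reproduces, with 9 = 10 nominal days − 1.

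**Inputs.** Insertion is on the morning of Day 1, during the OGTT (synopsis; Table 1; sections 4.1.2 and 5.2). Removal is at midday on Day 10 (section 5.3.4). Clock times are my assumption: insertion at hour h = 8, 10 or 12, removal at 12:00.

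**Formulas.** Wear = 9 × 24 + (12 − h) hours. Usable days U = (wear − 24)/24. Score for perfect wear = U/9. Bar as a share of obtainable wear = 7.2/U. Tolerated loss = (U − 7.2) × 24 hours.

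| Insertion | Wear (h) | U (days) | U/9 | 7.2/U | Tolerated loss (h) | 0.8 × U (days) |
|---|---|---|---|---|---|---|
| 08:00 | 220 | 8.17 | 90.7% | 88.2% | 23.2 | 6.53 |
| 10:00 | 218 | 8.08 | 89.8% | 89.1% | 21.2 | 6.47 |
| 12:00 | 216 | 8.00 | 88.9% | 90.0% | 19.2 | 6.40 |

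**Whole 24-hour periods.** Eight are complete. 8/9 = 88.9% meets the bar and 7/9 = 77.8% does not, although 7/8 = 87.5% of the obtainable periods were captured.

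**Sensitivity to clock times.** With insertion at 07:00–12:00 and removal at 11:00–13:00, U is 7.96–8.25 days and the bar is 87.3–90.5% of obtainable wear. The whole-period count stays at eight unless removal falls at an earlier clock time than insertion (12:00 in, 11:00 out), when it drops to seven.

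**Readings under which the stated 80% holds.**

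- Wear of 240 hours: U = (240 − 24)/24 = 9.0, and 7.2/9.0 = 80.0%.
- A nominal count of Days 2 to 10 in which part-covered days are accepted: nine days, and 7.2/9 = 80.0%. Both Day 2 (before the 24-hour point) and Day 10 (after midday) are incomplete. If only fully covered calendar days counted, Days 3 to 9 would give seven, and 7/9 = 77.8%.

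**Day numbering.** Were the visit Day 0, U would be 9.00–9.17 days and the bar 78.5–80.0%. Table 1, section 4.2.1 and the heading of section 5.3 make the visit day the first day, so this does not apply.

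**The case against.** The strongest reply is that H1a counts days, not hours. The protocol uses nominal days elsewhere: the challenges fall between Days 3 and 9, and the ActiGraph incentive requires 8 of 10 days. Drop the first and nine remain, so 7.2 is exactly 80%. The operative sentence asks for adequate data; only the hypothesis label asks for complete data. And if ten days of wear means 240 hours, the divisor is right as written.

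Much of this stands. The multiplication is correct, and a nominal count with part-days accepted is a coherent reading. A reader might infer that the operative bar simply is 88–90%; the documents do not support that, because they never say that days are measured as elapsed time. What does not stand is that the plan already resolves the matter. It omits a number of hours, leaves adequate undefined, has no part-day rule, and sets a removal time that falls short of 240 hours.

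A reader might also infer that a participant who loses 24 hours fails the criterion. The plan does not say whether the 80% is a cohort mean or applies to each participant; under a mean, one lost day is diluted. Early removal for discomfort is allowed, but no rate is given, so how likely a wrongly negative verdict is cannot be stated.

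**Conclusion.** The divisor of a primary feasibility threshold does not match the plan's own wear schedule when wear is read as elapsed time or 24-hour periods. About 8.0–8.2 days can be obtained, not 9; perfect wear scores 89–91%; and 7.2 days is 88–90% of what can be captured. This rests on the visit being Day 1, insertion at 08:00–12:00 and removal at 12:00, and it changes little for nearby clock times. It is conditional on the reading: with 240 hours of wear, or with Days 2 and 10 both accepted as adequate, the bar is 80% as stated.

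The direction is conservative: feasibility becomes harder to declare, not easier. H1a is a descriptive threshold with no hypothesis test, so the consequence is confined to the feasibility verdict. It should be corrected because that verdict is primary and the correction is small.

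**What to change.** Before the CGM data are seen, reconcile the ten days of wear (section 4.2.1; synopsis, Study Duration) with midday removal on Day 10 (section 5.3.4). Then make the divisor equal the scheduled wear after the omitted 24 hours, by one of two routes:

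- Keep the count of adequate days and divide by the number of 24-hour periods scheduled. Under the current schedule that is 8, with a bar of 0.80 × 8 = 6.4.
- Keep 9 and 7.2, but only if scheduled wear is 240 hours or the text expressly counts part-covered Days 2 and 10.

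Either way, define an adequate day, and do not shorten the divisor when a sensor comes off early; otherwise early removal would cost nothing. Use the same wording in sections 7.4.1 and 6.2 and in the synopsis. It would help to state there whether the 80% is a cohort mean or a share of participants; that choice is the sponsor's. Replacing the day count with a proportion of time is not needed and would change the endpoint.

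The cost is wording only, since section 4.1.5 already provides for export of glucose values with timestamps. The downside should be stated openly. Under the current schedule, matching the divisor lowers the bar from 7.2 to about 6.4–6.5 days. On elapsed time, the tolerated loss rises from about 19–23 hours to about 38–39 hours (0.2 × U × 24). In whole periods for one participant, seven of eight would suffice where all eight are needed now.

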#### 6.1.2 Physical Examination

A study physician (pediatric endocrinologist) will review with the parent and child the child's current and past medical history, a review of systems, and family history (with particular attention to cardiovascular disease and diabetes). A focused physical examination will be conducted, including measurement of height, weight, waist circumference, hip circumference, pubertal staging, and pertinent physical findings associated with insulin resistance, including the presence of acanthosis nigricans, which will be recorded on a standardized form. Investigators will verify that the patient has been fasting for a minimum of 10 hours.

---

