### **7.5 Sample Size and Power**

The sample size for this pilot study balances feasibility with the likelihood of obtaining meaningful results for future studies. Assuming 20% drop-out or incomplete data, a sample size of 40 should lead to 32 evaluable subjects. This will allow for subgroup analyses, including by sex and physical activity strata (high versus low). This study will include nearly twice as many participants with known dysglycemia (or more if previously undiagnosed) as those without in order to maximize the ability to compare impaired glucose tolerance and abnormal CGM-measured glucose trends.

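### Neither primary feasibility rule requires an evaluable home glucose challenge, so both can be met without one

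*Combined protocol and SAP*

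**What the plan says.** Section 7.1 defines the primary endpoint as "completeness of CGM data capture and adequacy of nutrition logs for evaluation of at-home glucose challenge". The objective that opens 7.4.1 likewise places data capture and logging on the days of the home challenges. Section 4.1.3 makes the glucose challenge the main comparison with the laboratory OGTT; 7.4.3 treats the mixed meal as exploratory.

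Two rules decide feasibility. They stand in 7.4.1 and are repeated in the synopsis and in 6.2.

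- **H1a:** "The number of days with adequate CGM data will be divided by 9, omitting the first 24 hours". The bar is 80%, or 7.2 days. An adequate day is not defined, and the text does not say whether the share is taken per participant or pooled.
- **H1b:** the hypothesis is ambitious: "Documentation of glucose and mixed-meal challenge will be complete and adequate for analysis for" at least 80% of participants. The next sentence counts those who document both challenges, including meal content. The decision sentence after it accepts the date and time of either challenge, or both. The synopsis gives the denominator as 40.

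H2 (7.4.1) takes the logged time of the glucose drink and reads the CGM 2 h 5 min later. Under 7.4.4, CGM gaps longer than 20 minutes stay missing.

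For the laboratory OGTT, "Investigators will verify that the patient has been fasting for a minimum of 10 hours" (6.1.2). For the home challenge, 5.3.2 instructs a fast of at least 10 hours and inactivity. Section 4.1.2 says the ActiGraph supplies "objectively measured activity and sleep data to define periods of eating, overnight fasting, and exercise". Section 7 sets no rule for a home challenge in which the instructions were not followed.

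**The concern.** A home test is usable only if the same participant supplies both pieces: a known time for the glucose drink, and CGM readings at that time and at 2 h 5 min. The plan counts the pieces separately and in different units, days for H1a and participants for H1b, and never joins them. H1b can also be satisfied by the wrong challenge.

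The study could therefore follow its rules exactly and conclude that home CGM-based evaluation is feasible while few participants produced a result that H2 can use. Because feasibility is the primary objective, its decision rule should measure what the conclusion will claim. The H1b decision sentence also conflicts with its own hypothesis, with the 7.4.1 objective and with 7.1.

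**Working it through.** **Inputs from the documents.** 40 participants (synopsis, 4.2.2); 9 counted CGM days each (7.4.1); both bars at 80% (7.4.1); 20% drop-out or incomplete data (7.5).

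**1. The plan's own figures.** 0.80 × 9 = 7.2 days. 40 × (1 − 0.20) = 32, as in "a sample size of 40 should lead to 32 evaluable subjects". Both reproduce.

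**2. H1b alone.** Suppose 32 participants log only the mixed meal and 8 log neither challenge. H1b = 32/40 = 80%, which passes. Usable glucose challenges: 0/40.

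**3. H1a alone.** Pooled, there are 40 × 9 = 360 participant-days. The bar is 0.80 × 360 = 288, so 72 days may be lost. If all 40 lose only the glucose-challenge day, (360 − 40)/360 = 320/360 = 88.9% of days remain and H1a passes. Usable glucose challenges: 0/40.

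**4. Both rules together.** Suppose 32 participants each log one challenge and lose CGM data on that day, and the other 8 log neither.
- H1b: 32/40 = 80%, passes.
- H1a, pooled: (360 − 32)/360 = 328/360 = 91.1%, passes.
- H1a, per participant: 7.2 means 8 whole days of 9. The 32 have 8/9 = 88.9% and the other 8 have 9/9, so all pass.
- Usable challenges of either kind: 0/40.

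**5. Illustration under a different reading.** If H1a were a share of participants with CGM data at the challenge, and H1b concerned the glucose drink, two 80% criteria would overlap in at least 0.8 + 0.8 − 1 = 60% (24/40; exact 95% interval 43.3% to 75.1%). Under independence the overlap is 0.8 × 0.8 = 64% (25.6/40), and at most it is 80% (32/40). The documents state neither condition.

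**6. Effect of the either-challenge wording.** Assume, since the documents give no rates, that each challenge is logged independently with probability g, and that CGM data are present at the glucose challenge with probability 0.8. The share logging at least one is 1 − (1 − g)².

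| g | At least one logged | Chance H1b passes (32 or more of 40) | Usable glucose challenges (g × 0.8) |
|---|---|---|---|
| 0.50 | 75% | 0.30 | 40% |
| 0.55 | 79.75% | 0.58 | 44% |
| 0.60 | 84% | 0.82 | 48% |

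At g = 0.60, glucose logging alone would reach 32 of 40 with probability 0.006.

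**7. A joint measure against the 80% benchmark.** At 32/40 the exact 95% interval is 64.4% to 90.9%. The probability of observing 32 or more of 40 is 0.006 if the true usable rate is 60%, 0.022 at 64%, 0.593 at 80% and 0.985 at 90%.

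**The case against.** The strongest reply is that the intent is tied to the challenges. The H1b hypothesis asks for documentation fit for analysis, the 7.4.1 objective names the challenge days, and the H1a rule requires adequate data on most days. It would be unfair to say that any CGM days and any logged time suffice; both rules carry an 80% bar. This stands as a description of intent. But the decision sentences do not carry the intent through, and they determine the conclusion.

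A second reply is that this is a pilot, component criteria are a reasonable choice, and the number analysed in H2 would reveal a shortfall. That is partly true, but the H2 count plays no part in the feasibility decision.

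A third is that a joint 80% standard is much stricter. Under independence, two components would each need about 89% (√0.8 = 0.894), and a true joint rate of 80% gives 32 or more of 40 with probability only 0.593. This stands. It is a reason to report the proportion with its interval and to treat 80% as a benchmark.

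On fasting, 4.1.2 assigns ActiGraph data, not food logs, to defining eating and fasting periods, and 7.4.1 already plans correlation subgroups by activity level and prior-day carbohydrate intake. With surveys three times a day, a blank entry cannot separate a kept fast from an unrecorded meal. Fasting therefore does not belong in the definition of an evaluable challenge; a sensitivity analysis is the right place for it.

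**Conclusion.** The point holds: no primary rule requires CGM readings at a logged glucose challenge in the same participant, and both rules can pass with 0 of 40 usable. That result follows from the written rules alone, under either reading of H1a. It shows what the rules permit; it does not predict what will happen.

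Three stronger inferences are not supported.

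- A reader might take 60% as the worst case. That figure treats the day-based H1a as a share of participants and ignores the either-challenge wording of H1b. It is one scenario, and the rules set no floor.
- A reader might treat the 32 in 7.5 as a promised number of evaluable challenges. It is a planning allowance for drop-out and incomplete data combined.
- A reader might lower the usable share further for broken fasts. The documents give no rate for this, so no figure is offered.

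**What to change.** Keep H1a and H1b, and amend 7.4.1, with matching text in the synopsis and 6.2, as follows.

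1. Add as a primary feasibility measure the proportion of all 40 participants with an evaluable home glucose challenge: a documented glucose ingestion time on Days 3-9, and CGM values at ingestion and at 2 h 5 min after the 7.4.4 gap rule is applied. Report it with an exact 95% interval against the plan's 80% benchmark, and base any feasibility statement about the home glucose challenge on it.
2. Reconcile the H1b decision sentence with its hypothesis and with 7.1, so that a mixed-meal log alone does not count as documentation of the glucose challenge.
3. State whether H1a is per participant or pooled, and define an adequate day.
4. Run H2 on all evaluable challenges. Add a sensitivity analysis that excludes those where the food log or ActiGraph record positively contradicts the protocol's own fast or inactivity instruction. Treat blank logs as unknown and not as failures, and fix the ActiGraph criterion before analysis.

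The data are already being collected, so the work is plan wording and a derived flag per participant. The change does alter the basis of the primary conclusion, and the headline feasibility figure may be lower than under the present rules.
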